## 6.2 Study visits and diagnostic procedures

The table above lists only procedures which are specifically required for the evaluation of study aims and endpoints. Additional diagnostic and therapeutic procedures may be necessary according to clinical standard as defined in evidence-based AML treatment guidelines [NCCN guideline, Onkopedia-Leitlinie, Döhner et al 2010] and according to the investigator's clinical experience and expertise.

## 6.3 Assessment of safety

Regular safety assessment will ensure that patients have no or minimal study related risk. Safety evaluations will include results of physical examinations (including neurological disorders), vital signs (blood pressure, heart frequency, temperature), AEs, concomitant medications, and abnormal laboratory tests.

The following parameters will be used for safety assessment:

- Rate of early deaths (within 14 and 30 days) and induction deaths (until day 60 or until the beginning of next treatment – whichever occurs first)
- Incidence of serious infectious complications (Grades 3-5 CTCAE V5.0)

## 6.4 Assessment of efficacy

Response and progression of leukemia subjects will be evaluated in this study based on local results of bone marrow aspirates / biopsies / peripheral whole blood. Response assessment in this study will be based on the revised recommendations of the International Working Group for diagnosis, standardization of response criteria, treatment outcomes, and reporting standards for therapeutic studies in AML (Cheson et al, 2003, Döhner et al, Blood 2017).

A central review will be performed for cytomorphological examinations and immunophenotyping for MRD assessment in the Hematology Lab in Dresden and is used for quality control.

### 6.4.1 Bone marrow assessments

Bone marrow assessments should be done preferentially as aspirations. Bone marrow biopsies are only necessary in case of dry puncture and the inability to aspirate bone marrow ("punctio sicca").

Bone marrow assessment includes:

- Cytomorphological examination including cytochemistry
- Immunophenotyping
- Cytogenetics (incl. FISH)
- Molecular genetic analyzes for the presence of FLT3-ITD mutation, genomic ratio of the presence of FLT3-ITD vs. FLT3-WT, for nucleophosmin mutations (NPM1) including

NPM1 MRD, for the presence of BCR-ABL1, PML-RAR $\alpha$ , RUNX1-RUNX1T1 and CBF $\beta$ -MYH11, double-CEBPA, ASXL1, RUNX1, TP53 mutations.

The quality of all participating laboratories will be assured by checking the installed quality management systems and checking the availability of certificates for regular participation on External Quality Assessments (Ringversuche).

### **Central Review**

The cytomorphologic examinations and immunophenotyping for MRD analysis (FACS) also will be done centrally in the Hematology Laboratory in Dresden.

The required material for the analyses is:

- **Cytomorphology:** at minimum 2 peripheral blood and 2-6 bone marrow smears (unstained)
- **FACS:** 10ml heparinized bone marrow

Please ship the samples preferably from Monday – Thursday; shipment on Friday should be avoided.

## **6.4.2 Response criteria**

### **6.4.2.1 Early Response Assessment on day 18 – 21 of V-MAC**

For early response assessment, only cytomorphology including cytochemistry is required.

**Good response:**

Reduction in bone marrow blast count to below 5% (aspirate with marrow spicules)

**Moderate response:**

Reduction in bone marrow blast count, blast count  $\geq 5\%$  (aspirate with marrow spicules)

**Refractory disease:**

Increase in bone marrow blast count compared to baseline or No change in bone marrow cellularity with unchanged blast count

**6.4.2.2 Remission assessment**

Remission assessment will follow standard criteria according to Döhner et al., 2017 and will be done 28-45 days after start of V-MAC (depending of blood count recovery), but has to be done latest on day 45 irrespective of the blood count regeneration.

If regeneration blasts are suspected, bone marrow aspiration should be repeated, but not later than day 45 from start of V-MAC. Only the final remission assessment will be documented in the eCRF.

To define the real number of platelets and neutrophils, a period of at least 2 days without transfusion or treatment with G-CSF is necessary to determine a CR or CRi.

**Morphologic complete remission (CR):**

- Platelet count  $>100,000/\mu\text{l}$
- Granulocyte count of  $>1,000/\mu\text{l}$
- Bone marrow (aspirate with marrow spicules):  $< 5\%$  blasts,
- Absence of circulating blasts and blasts with Auer rods
- Absence of extramedullary leukemia
- Transfusion independent stable hemoglobin value

**Complete remission with incomplete recovery (CRi):**

All CR criteria are fulfilled except for residual neutropenia (granulocyte count  $\leq 1000/\mu\text{l}$ ) and/or thrombocytopenia (platelet count  $\leq 100.000/\mu\text{l}$ ).

**Complete remission with incomplete platelet recovery (CRp):**

All CR criteria are fulfilled except for residual thrombocytopenia (platelet count  $\leq 100.000/\mu\text{l}$ ).

**Treatment Failure:**Resistant Disease:

Failure to achieve CR or CRi only includes patients surviving  $\geq 7$  days following completion of initial treatment, with evidence of persistent leukemia by blood and/or bone marrow examination

Morphologic relapse:

Reappearance of blasts in PB or bone marrow blasts  $\geq 5\%$  after achievement of complete remission or occurrence of extramedullary disease

Molecular relapse

If MRD can be assessed in the individual patient by multicolour flow cytometry and/or PCR methodology, the patient achieves MRD negative status in CR, the reoccurrence of the previously identified MRD marker in a patient with CR defines a molecular relapse.

Death in aplasia:

Deaths occurring  $\geq 7$  days following completion of initial treatment while cytopenic; with an aplastic or hypoplastic bone marrow obtained within 7 days of death, without evidence of persistent leukemia

Death from indeterminate cause:

Deaths occurring before completion of therapy, or  $< 7$  days following its completion; or deaths occurring  $\geq 7$  days following completion of initial therapy with no blasts in the blood, but no bone marrow examination available

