**DLTs are defined as:**

- 1) Any non-hematologic grade 3-5 toxicities related to venetoclax exposure
- 2) Clinical TLS (see [Appendix 3](#))
- 3) Hematologic toxicities CTCAE grade 4 not recovered by day 45 in the presence of <5% bone marrow blasts (leukemia-free state):
  - neutropenia (ANC  $<0.5 \times 10^9/L$ ) or
  - thrombocytopenia (platelets  $< 25 \times 10^9/L$ )

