#### **Reasons for patient's premature end of study might be:**

- At their own request or at the request of their legally acceptable representative
- If, in the investigator's opinion, continuation of study would be harmful to the subject's wellbeing or if the subject is no longer eligible for the study (e.g. development of any intercurrent illness).
- At specific request of the sponsor and in liaison with the investigator (e.g. obvious non-compliance, safety concerns)
- Use of illicit drugs or other substances abuse that may, in the opinion of the investigator, have a reasonable chance of contributing to toxicity or otherwise confound the results
- Subjects who experience a relapse or are diagnosed with resistant disease throughout the trial, unless the investigator (in consultation with the sponsor) deems that continued treatment is appropriate.
- The development of a second malignancy that requires a different treatment
- Interruption of venetoclax >28 days during maintenance therapy

A withdrawn subject is referred to as either "screening failure" or "dropout (= premature end of treatment)" depending on the time point of withdrawal.

A subject who discontinues study treatment prematurely for any reason is defined as a “dropout” if the subject has already been administered at least 1 dose of the study drug. Data of drop-out patients will be analyzed intention-to treat as part of the full analysis set (FAS), see [section 8.2.2.1](#).

A subject who, for any reason (e.g. failure to satisfy the selection criteria), terminates the study prior to the first dose of study drug is regarded as a “screening failure”.

In all cases, the reason for withdrawal must be recorded in the electronic case report form (eCRF) and the subject’s medical record. If a patient has withdrawn his consent, it has also to be documented in the subject’s medical record whether the patient has agreed to further documentation of personal data during follow-up period.

Treatment with the Investigational medicinal product (IMP) venetoclax should be stopped for the following reasons and has to be reported in the appropriate page of the eCRF:

- Severe allergic reactions, such as exfoliate erythroderma, anaphylaxis, or vascular collapse, related to the study drug
- Experience of DLT
- Subjects with a beta human chorionic gonadotropin test consistent with pregnancy. Pregnancy will be reported along the same timelines as SAEs (see [section Reporting of SAEs and SARs](#)).

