## **5.4.3 Treatment schedule in the maintenance therapy**

Patients who achieve a CR/CRp with ANC recovery ( $ANC \geq 1000/\mu L \geq 1 \times 10^9/L$ ) may receive venetoclax maintenance treatment up to twelve 28-day cycles if they have no other post-remission treatment options (e.g. auto/allo-TX, chemo-consolidation therapy etc.).

Venetoclax will be given at dose 400 mg QD per os as continuous treatment starting within 14 days after the End of Treatment assessment of previous treatment phase up to 12 cycles. Duration of one cycle is 28 days.

If co-administration with strong and moderate CYP3A inhibitors daily dose will be reduced according to section [5.5](#).

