#### 5.4.4 Dose modifications during V-MAC in expansion and maintenance treatment

The following dose reduction rules shall be applied in case toxicities occur.

In case of either one of these toxicities, venetoclax shall be stopped and re-started according to the recommended dose modifications in Table 3 and Table 4. If co-administration of strong or moderate CYP3A inhibitors, venetoclax dose modification has to be done according to [Table 5](#) and [Table 6](#).

In maintenance therapy, dose reductions according to [Table 3](#), [Table 4](#), [Table 5](#), [Table 6](#) are necessary if either one of the below occurs in patients with CRp:

- ANC falls <1000/ $\mu$ L or
- PLT count falls <50,000/ $\mu$ L or
- Toxicities grade  $\geq$  3

Table 3: Recommended Dose Modifications for Toxicities during V-MAC in expansion and maintenance

Event	Occurrence	Action
Non-Hematologic Toxicities		
Grade 3 or 4 non-hematologic toxicities	1 st occurrence	Interrupt venetoclax. Once the toxicity has resolved to Grade 1 or baseline level, venetoclax therapy may be resumed at the same dose. No dose modification is required.
	2 nd and subsequent occurrences	Interrupt venetoclax. Follow dose reduction guidelines in Table 4 when resuming treatment with venetoclax after event has resolved to grade 1.

Hematologic Toxicities (only during maintenance)		
Grade 3 or 4 neutropenia with infection or fever; or Grade 4 hematologic toxicities (except lymphopenia)	1 st occurrence	Interrupt venetoclax.  To reduce the infection risks associated with neutropenia, granulocyte-colony stimulating factor (G-CSF) may be administered with venetoclax if clinically indicated.  Once the toxicity has resolved to Grade 1 or level on day 1 of maintenance, venetoclax therapy may be resumed at the same dose.
	2 nd and subsequent occurrences	Interrupt venetoclax. Consider using G-CSF as clinically indicated. Follow dose reduction guidelines in Table 4 when resuming treatment with venetoclax after event has resolved to Grade 1 or on day 1 of maintenance.

Table 4: Dose Modification for Toxicity during Venetoclax Treatment

Dose at interruption, mg	Restart dose, mg
400	300
300	200
200	100
100	50
50	Stop study drug permanently

Table 5: Dose Modification for Toxicity during Venetoclax Treatment in case of **Co-medication with strong CYP3A inhibitors**

Dose at interruption, mg	Restart dose, mg
100	50
50	20
20	10

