Cycle day	Maintenance pre-visit (only done, if V8 of previous treatment phase >14 days)	Eligibility	Cycle 1		End of Cycle 2, 4, 6, 9	End of Cycle 12 = EOS or at Premature EOS f	Post-study Follow-up g
		day -7 to -1	d1	d15	d28 (+/-5days)	d28 (+/-5days)	every 3 months
Physical exam, ECOG	x		x	x	x	x	
Vital Signs, body weight h	x		x	x	x	x	
Full Blood Count a	x		x	x	x	x	
Chemistry and Coagulation b	x		x	x	x	x	
β-HCG pregnancy test		x					
Bone marrow assessment c,d	x				x	x	
Material for central Review e	x				x	x	
ancillary research material i					x	x	
Concomitant Medication	x		continuous till day 28 after last dose of IMP				
Adverse Events	x		continuous till day 28 after last dose of IMP				
Disease status & Survival							x

a Blood count (hemoglobin, hematocrit, white blood cells, platelets) incl. microscopic differential except C1D15. In addition, these evaluations should be done as often as necessary in the opinion of the treating physician

b Determination of: sodium, potassium, calcium, creatinine, urea, ALAT (GPT), ASAT (GOT), LDH, alkaline phosphatase, bilirubin, total protein, albumin, uric acid, INR, aPTT, fibrinogen.

c local bone marrow assessment: cytomorphology including cytochemistry, immunophenotyping, cytogenetics, molecular diagnostics

d Bone marrow assessment and peripheral complete blood count proving a CR/CRp (not CRi) is a prerequisite for the start of maintenance treatment. If CR/CRp is proven at the V8 and maintenance starts within 2 weeks after bone marrow assessment, no additional bone marrow is necessary.

e samples for central diagnostics (Hema Lab Dresden): 5 bone marrow and 2 peripheral blood smear slides for cytomorphology and 10 ml heparinized bone marrow for immunophenotyping

f If a subject discontinues the study for any reason (except for death or loss to follow-up), a premature end-of-study evaluation will be performed 7 to 14 days after the last dose of study drug.

g All patients will be followed-up after last study visit for survival, remission status, further AML therapies (regimes and start dates) and second primary malignancies for minimum 24 months, either by phone calls or visits

h vital signs: blood pressure, heart frequency and temperature

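### Maintenance entry as CRp carries no platelet condition and is not reconciled with the 50,000/µL reduction limit in section 5.4.4, with Table 3, or with a prior DLT

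*Protocol*

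**What the plan says.** **Response category.** Under protocol section 6.4.2.2, CRp means "All CR criteria are fulfilled except for residual thrombocytopenia", with platelets at or below 100,000/µl. No lower limit is given.

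**Entry to maintenance.** Section 5.4.3 addresses "Patients who achieve a CR/CRp with ANC recovery" (ANC at least 1 × 10^9/L) who have no other post-remission treatment option. On dose it says: "Venetoclax will be given at dose 400 mg QD per os as continuous treatment starting within 14 days". The only dose adjustment at entry is for CYP3A inhibitors. Sections 3.3 and 3.4 use the same response and ANC condition and call 400 mg a maximum; 3.4 repeats the restriction to patients without another option. Table 10 footnote d says that marrow and blood count "proving a CR/CRp (not CRi) is a prerequisite for the start of maintenance treatment". None of these places gives a platelet condition or mentions an earlier DLT.

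**Dose reduction in maintenance.** The text of section 5.4.4 says that dose reductions under Tables 3 to 6 "are necessary if either one of the below occurs in patients with CRp". The list that follows includes a platelet count that falls below 50,000/µL.

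**Table 3.** For haematologic toxicity in maintenance, the table acts on grade 4 events, or on grade 3–4 neutropenia with infection or fever. At a first occurrence venetoclax is interrupted and may resume at the same dose once the toxicity is back to grade 1 or to the level on day 1 of maintenance. The reduction steps of Table 4 apply from the second occurrence.

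**DLT, phase I.** Under section 3.2, grade 4 haematologic toxicity (for platelets, below 25 × 10^9/L) is a DLT if "not recovered by day 45 in the presence of <5% bone marrow blasts (leukemia-free state"). Section 4.4.1 lists "Experience of DLT" among the reasons for which venetoclax should be stopped.

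**The concern.** The entry rule and the reduction rule address the same group, CRp patients on maintenance. One has no platelet condition; the other treats a platelet count below 50,000/µL as grounds for a necessary reduction. Investigators with the same count in front of them could therefore act differently depending on the section they follow.

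Two things are at stake. The first is safety: these are patients with marked thrombocytopenia starting up to twelve 28-day cycles of continuous venetoclax. The second is interpretability. Sections 8.1.5.1 and 8.2.7.1 report exposure as a percentage of planned dose and duration, and adverse events are tabulated by grade. If sites apply the entry and reduction rules differently, maintenance exposure and the rate of thrombocytopenia on maintenance partly reflect that difference.

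**Working it through.** The plan gives no figure on this point, so the check takes one patient through each rule.

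**Inputs (all from the protocol)**

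- CR requires platelets above 100,000/µl and a "Granulocyte count of" more than 1,000/µl; CRp relaxes only the platelet criterion (6.4.2.2).
- Remission is assessed by day 45 at the latest, whatever the blood counts (6.4.2.2). Low platelet counts at that visit are therefore foreseen.
- Entry: CR/CRp, ANC at least 1 × 10^9/L, no other post-remission option (5.4.3).
- Reduction limit in the text of 5.4.4: platelets below 50,000/µL, that is 50 × 10^9/L.
- Grade 4 thrombocytopenia, as used in the DLT definition: below 25 × 10^9/L (3.2).
- A full blood count is scheduled on day 1 of maintenance cycle 1 (Table 10).

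**Mapping.** Assume ANC above 1,000/µl, marrow blasts below 5% and all other CR criteria met. The maintenance columns assume that the same platelet count is found on day 1 of maintenance.

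| Platelets (× 10^9/L) | Response | Maintenance entry open? | Below the 5.4.4 text limit? | Table 3 acts? | Phase I DLT criterion at day 45? |
|---|---|---|---|---|---|
| above 100 | CR | yes | no | no | no |
| 50 to 100 | CRp | yes | no | no | no |
| 25 to below 50 | CRp | yes | yes | no | no |
| below 25 | CRp | yes | yes | grade 4 | can be met |

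**Step 1: entry against reduction.** Take a patient at 30 × 10^9/L. Entry is open at 400 mg. At the day-1 count the patient is already below 50. If *falls* in 5.4.4 means *is*, a reduction is called for at the first dose, although 5.4.3 gives 400 mg. If it means a drop from 50 or above, the trigger cannot apply while the patient stays below 50. The rule then leaves out the patients with the lowest counts at entry. The text does not say which is meant.

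**Step 2: text against Table 3.** For the same patient at 30, Table 3 does nothing, because the count is not grade 4. The text above the table calls a reduction necessary and refers to that table for it. At 20 × 10^9/L Table 3 does act, but a first occurrence leads to interruption and resumption at the same dose, not to a reduction. Its return-to-day-1 criterion also means that, with no platelet condition at entry, there is no fixed platelet level for restarting.

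**Step 3: prior DLT, phase I only.** Section 3.7 foresees maintenance for phase I patients. Venetoclax within V-MAC ends on day 14, or day 10 at dose level -1 (5.4.1). A haematologic DLT established at day 45 comes after that, so the only trial venetoclax left to stop is maintenance. Section 4.4.1 keeps stopped patients on the visit schedule until V8 but does not say whether maintenance is closed to them, and no entry passage says so either.

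**Step 4: primary endpoint.** CR/CRi is determined at V8, before maintenance begins. Neither the response rate nor its test depends on any of these rules.

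**The case against.** **The reduction rule concerns events on treatment.** Section 5.4.4 speaks of events in maintenance and of counts that fall. Section 7.1.1 does not treat a finding unchanged from baseline as an adverse event, and Table 3 accepts the day-1 level as a restart level. This stands to the extent that the day-45 count itself triggers no reduction. It does not remove the gap, because on that reading a patient who enters below 50,000/µL has no platelet limit from 5.4.4 at all.

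**Entry is a permission.** The entry passages say that patients *may* receive maintenance, sections 3.3 and 3.4 call 400 mg a maximum, and 3.4 and 5.4.3 confine maintenance to patients with no other option. An investigator can decline. This stands and narrows the group, but it leaves the decision to each site without a stated criterion.

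**The DLT stop can be read as overriding the permission.** That is a sensible reading, and follow-up only until V8 is consistent with it. The criterion is also conditional: section 3.2 requires attribution to venetoclax and excludes toxicity attributed to AML-related illness listed in Appendix 5, which includes thrombocytopenia. All of this stands. What remains is that the entry passages do not say it.

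**A stronger reading.** A reader might infer that a single day-45 count at once qualifies a patient for full dose, requires a reduction and stops the drug. The documents do not support that. The reduction rule operates only within maintenance, entry is optional, and the stop is limited to phase I and depends on attribution. A reader might also apply some share of low-platelet CRp to the expected phase II responders (0.65 × 42 = 27.3) to count the patients affected. No such share is in the protocol. Responders are also the wrong denominator, since those with a transplant or consolidation option are not candidates for maintenance.

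**Conclusion.** The point holds as a gap and inconsistency in wording, in three parts.

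- Entry has no platelet condition while 5.4.4 has a limit at 50,000/µL for the same CRp patients. This applies to patients of either phase who enter maintenance as CRp below that level.
- The text of 5.4.4 and Table 3 disagree on platelets. Between 25 and below 50 × 10^9/L one calls for a reduction and the other for nothing. Below 25, one calls for a reduction and the other, at first occurrence, for interruption and the same dose.
- In phase I, which plans at most 18 patients, a CRp patient below 25 × 10^9/L at day 45 can also have had a DLT. How that bears on maintenance entry is not stated.

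The number of patients concerned cannot be derived from the documents and may be small. The primary endpoint and its test are unaffected. The consequences are for patient safety in maintenance and for the interpretation of maintenance exposure and toxicity. The conclusion rests only on the protocol text. It does not fault the CRp definition as a response category; the gap is in using it as the sole platelet-related entry condition. The passages should be reconciled.

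**What to change.** By amendment, reconcile the maintenance entry condition (sections 3.3, 3.4 and 5.4.3, and Table 10 footnote d) with the 50,000/µL limit in section 5.4.4. State whether that limit applies to a patient already below it on day 1 of maintenance. Bring the text of 5.4.4 and Table 3 into agreement on what a given platelet count leads to. State in 4.4.1 or 5.4.3 how a prior DLT bears on entry to maintenance. The aim is that one platelet count leads to one instruction.

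Which platelet rule, dose or stopping rule applies is a clinical decision for the sponsor, and none is proposed here.

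The cost is wording only. Platelets are already measured at V8, at the maintenance pre-visit where one is needed, and on day 1 of cycle 1, so no visit or test is added and the sample size is unchanged.
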